##### **4.5.2.1 Definitions and Derivations**

All summaries of clinical chemistry and hematology variables will be based on samples analyzed at the central laboratory and presented in SI units.

**Hyper- and hypokalemia:** Based on the S-K obtained from the central laboratory at visit 8, a set of classification variables reflecting different degrees of hyperkalemia ( $> 5.0$ ,  $> 5.5$ ,  $> 6.0$  mmol/L,  $> 6.5$  mmol/L) and hypokalemia ( $< 3.5$ ,  $< 3.0$ ,  $< 2.5$  mmol/L) will be created.

**Lab abnormalities:** Abnormality status (“low”, “high”) of the laboratory values will be derived based on the normality ranges provided by the central laboratory.

**Vital signs abnormalities:** Abnormal vital signs will be indicated directly in the eCRF by the investigator.

##### **4.5.2.2 Presentations**

###### **Summary of measurements over time**

The result and the change from baseline of each clinical chemistry and vital sign variable will be summarized, by treatment group, at baseline and 12-month visit (for labs) or EOIV/PIDV (for vital signs), using descriptive statistics as appropriate for continuous variables. For the ECG variables, only the baseline measurements will be presented, with no change from baseline, as there are no planned post-baseline ECG measurement occasions. The absolute values, as well as the changes, will also be illustrated by means of box plots.

### **Haematology, clinical chemistry and vital signs, treatment emergent abnormalities**

The number, and percentage, of subjects falling into the different categories as defined above, at any post-baseline visit including unscheduled, for each variable, will be tabulated. The number of subjects with a baseline and a post-baseline value in the respective treatment arms will be used as the denominator for the calculation of the percentages.

The tabulations will be replicated for on-treatment time period.

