#### **Type of Participant and Disease Characteristics**

- 4 Receiving hemodialysis (or hemodiafiltration) 3 times a week for treatment of ESRD for  $\geq$  4 months before enrollment

- 5 Must have hemodialysis access consisting of an arteriovenous fistula, arteriovenous graft, or tunneled (permanent) catheter which is expected to remain in place for the entire duration of the study
- 6 At least 2 out of 2 or 2 out of 3 pre-dialysis S-K values  $\geq 5.5$  mmol/L after the LIDI during screening

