**Table 7      Laboratory Safety Variables**

Clinical Chemistry (Serum)	Hematology/Hemostasis (Whole Blood)
S-Sodium	B-Leukocyte count a
S-Bicarbonate	B-Leukocyte differential count (absolute count and %) a
S-Phosphate	B-Platelet count a
S-Blood urea nitrogen	
S-Magnesium	
S-Creatinine a	
S-Bilirubin, total a	
S-Alkaline phosphatase a	
S-Aspartate transaminase a	
S-Alanine transaminase a	
S-Gamma-glutamyl transferase a	
S-Albumin a	
S-Chloride a	
S-Creatine kinase a	
S-Glucose a	
S-Lactate dehydrogenase a	
S-Total protein a	
S-Pregnancy test (serum HCG) b	

Blood B; Human chorionic gonadotropin HCG; Red blood cell RBC; Serum S.

a Randomization/Day 1 Visit 4 only.

b Screening Visit 1 only. Repeated serum HCG pregnancy tests may be analyzed by the local laboratory.

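### The SAP's treatment emergent abnormality table sets no baseline condition, so subjects already abnormal at baseline are reported as treatment emergent

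*SAP*

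**What the plan says.** The table stands in SAP 4.5.2.2 under the heading "Haematology, clinical chemistry and vital signs, treatment emergent abnormalities". Four parts of the plan bear on it.

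- **Numerator (SAP 4.5.2.2).** It counts, with percentages, those "falling into the different categories as defined above, at any post-baseline visit including unscheduled, for each variable, will be tabulated". The table is repeated for the on-treatment period.
- **Categories (SAP 4.5.2.1).** Low or high status "will be derived based on the normality ranges provided by the central laboratory". For vital signs, the investigator marks abnormality in the eCRF.
- **Denominator (SAP 4.5.2.2).** "The number of subjects with a baseline and a post-baseline value in the respective treatment arms will be used as the denominator".
- **Sampling.** SAP 4.5.2 puts central chemistry at Visits 1 to 4 and Visit 8, and vital signs at Visits 1 and 4 and at EOIV or PIDV. Footnote a of Protocol Table 7 marks many variables "Randomization/Day 1 Visit 4 only". SAP 4.5.2.2 nevertheless states, for the baseline and 12-month summaries, "The result and the change from baseline of each clinical chemistry and vital sign variable will be summarized".

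Neither document defines treatment emergent for laboratory or vital-sign data, and neither plans a baseline-by-post-baseline shift table. SAP 3.4.1.4 defines only the during-study and on-treatment periods.

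**The concern.** A treatment emergent abnormality is ordinarily one that was not there before treatment. The rule as written does not ask that question. A subject who is high at randomization and still high at Visit 8, even if improved, goes into the numerator.

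The population makes this more than a technicality. Everyone has ESRD on hemodialysis, and entry requires "At least 2 out of 2 or 2 out of 3 pre-dialysis S-K values" at or above 5.5 mmol/L. The protocol's target is 4.0 to 5.0 mmol/L, so high potassium before the first dose is to be expected in many subjects. The same is plausible for other pre-dialysis analytes, though the documents give no rates.

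Clinical laboratory variables are a stated safety endpoint (Protocol Section 3, Table 3). At stake are a label that describes pre-existing disease as an on-study finding, and a comparison of new-onset abnormality in which a real arm difference is harder to see.

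**Working it through.** **1. Text check.** The documents state no figure for this table, so there is none to reproduce. Set side by side, the numerator has no baseline term, the categories have no baseline term, and the denominator requires only that a baseline value exists. SAP 3.4.1.5 defines baseline (last value on or before randomization), but this table does not use it for comparison. The on-treatment repeat narrows the time window and still adds no baseline condition.

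**2. Effect on the displayed percentages.** Let p0 be the proportion in a category at baseline (equal between arms in expectation, by randomization), s the proportion of those still in it afterwards, and q the new-onset proportion among the rest.

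- Displayed proportion in an arm = p0·s + (1 - p0)·q.
- With equal s, arm difference displayed = (1 - p0)·(q1 - q2).

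The inputs p0, s and q are assumptions; none is in the documents. Take s = 90% and q = 15% v 10% (true ratio 1.50). For example, at p0 = 50%: 0.45 + 0.5 × 0.15 = 52.5% and 0.45 + 0.5 × 0.10 = 50.0%.

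| p0 | Displayed | Ratio | Counted subjects who were abnormal at baseline |
|---|---|---|---|
| 10% | 22.5% v 18.0% | 1.25 | 44% |
| 30% | 37.5% v 34.0% | 1.10 | 76% |
| 50% | 52.5% v 50.0% | 1.05 | 88% |
| 70% | 67.5% v 66.0% | 1.02 | 94% |
| 90% | 82.5% v 82.0% | 1.01 | 98% |

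The last column is p0·s divided by the mean of the two displayed proportions; at p0 = 50%, 0.45 / 0.5125 = 88%.

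A second assumed set (s = 85%, q = 30% v 20%) behaves the same way: 57.5% v 52.5% at p0 = 50%, 68.5% v 65.5% at 70%, and 79.5% v 78.5% at 90%.

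With an at-risk numerator and denominator, the first set shows 15% v 10% at every p0.

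**3. Where the drug changes persistence.** Equal s is doubtful for potassium, which SZC is meant to lower. Assume p0 = 90%, s = 50% v 75% and q = 20% v 40% (SZC v placebo). The literal rule gives 0.45 + 0.02 = 47.0% against 0.675 + 0.04 = 71.5%. The difference stays plain, although most of those counted were already high at baseline. In this case an at-risk denominator would keep only 10% of subjects, for example 100 of an assumed 1000 evaluable per arm.

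**4. Which variables have a later value.** Protocol Table 7 lists 19 chemistry analytes (excluding the pregnancy test) and 5 haematology variables. Footnote a applies to 12 of the 19 and to all 5, so 12 + 5 = 17 of 24 have no scheduled post-baseline sample. The 7 that remain are potassium, calcium, sodium, bicarbonate, phosphate, urea nitrogen and magnesium.

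**The case against.** The strongest reply is that the heading, together with a denominator that requires a baseline value, shows that a comparison was intended. That may be so. But the comparison is nowhere written, and a programmer who follows the stated rule produces the wrong table. The intention supports the fix and does not make it unnecessary.

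A second reply is that the table is descriptive, with no test planned, and that other outputs show arm differences. These are the change-from-baseline summaries and box plots, the graded hyper- and hypokalemia table at Visit 8 and the S-K distribution in SAP 4.2.2. This stands in part and limits the harm. But the continuous summaries do not count subjects who newly leave the normal range, the graded table covers potassium only, and none of these outputs corrects the label.

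A reader might go further and infer that real arm differences are swamped, or that the table favours one arm. The documents support neither. They give no baseline abnormality rates or laboratory ranges. Randomization makes the effect dilution and not directional bias, and at low prevalence the dilution is modest.

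Nor does the entry criterion make every subject hyperkalemic at baseline. It concerns two of two or two of three screening values, and SAP 4.1.5.1 and 4.2.1.7 provide for a baseline S-K below 5.5 mmol/L.

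On the Day-1-only variables, the reply is that SAP 3.4.3 and this table keep unscheduled values. That also stands, and dropping those rows would lose safety information.

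**Conclusion.** The concern holds as a defect of definition and labelling. The stated rule reports pre-existing abnormalities as treatment emergent, and this follows from the text without any assumption. The rule counts subjects once per category, so the fault lies in who is counted and not in repeated values.

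Arm differences in new-onset abnormality are diluted by (1 - baseline prevalence) when persistence is equal between arms. In the illustration a true ratio of 1.50 appears as 1.25 at 10% prevalence and 1.01 at 90%. How large this is in the trial cannot be known from the documents, and it will vary by analyte. For potassium the dilution need not occur, since the drug may change persistence.

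A lesser, certain point is that the 12-month change summary is planned for every chemistry variable, while 12 of 19 have no scheduled 12-month sample.

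**What to change.** In SAP 4.5.2.2:

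- Count a subject as treatment emergent only if the category was absent at baseline and present post-baseline. The category is low or high for laboratory variables, and investigator-flagged abnormal for vital signs.
- Use as denominator the subjects not in that category at baseline who have a post-baseline value.
- Add a baseline-by-post-baseline shift table (low, normal, high) by arm. For S-K this will be the main informative display, because few subjects may be at risk for high.
- Limit the 12-month change-from-baseline summary to the 7 chemistry analytes sampled at Visit 8.
- Keep unscheduled central-laboratory values for the other variables in the abnormality table, marked as unscheduled only.

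Renaming the table as any post-baseline abnormality would cure the label but would leave the dilution.

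The cost is SAP wording, some programming and one extra table, with no new laboratory samples. For vital signs the rule needs the investigator's flag at baseline as well as afterwards; the documents do not say whether it is recorded at both, so this should be confirmed. The downside is smaller denominators per category, very small for high S-K.

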### **Instances of hyper- and hypokalemia**

Number, and percentage, of subjects experiencing different degrees of hyper- and hypokalemia at the 12-month visit, as defined above, will be tabulated. The number of subjects with observations available at visit 8 in the respective treatment arm will be used as the denominator for the percentages.

### **Listings**

The listings provided will include, but may not be limited to:

- Instances of lab measurements classified as abnormal.
- Instances of vital sign measurements classified as abnormal.

## **4.5.3 Other Safety Assessments**

### **4.5.3.1 Definitions and Derivations**

Pre-dialysis weight will be collected at Visit 1, 4 (randomization), and all the visits specified in the protocol. Post-dialysis weight from the previous dialysis session will be collected at Visit 4 (randomization), and all other visits specified in the protocol, except SCV.

**Interdialytic weight gain (IDWG)** will be calculated as the difference between current pre-dialysis weight and the previous post-dialysis weight (measured at proceeding dialysis session prior to the visit) in kilograms. If current pre-dialysis weight or previous post-dialysis weight is missing, no interdialytic weight gain will be derived.

### **4.5.3.2 Presentations**

An overview of pre-dialysis weight and IDWG over time will be created. That is, the result obtained at baseline and each scheduled post-baseline visit, as well as the change from baseline, will be summarized by treatment group as appropriate for continuous variables. The IDWG profile over time will also be illustrated by means of box plots.

## 5 INTERIM ANALYSES

The DMC will conduct interim analyses for futility and efficacy when respectively 40%, and 70% of the total number of primary endpoint events have accrued and have been adjudicated (i.e, a minimum of 292 and 511 events).

The futility threshold for non-binding futility analysis is defined as the estimated hazard ratio, SZC versus placebo being equal to or larger than 1. This will correspond to a predictive power of < 5.1%.

At the efficacy interim analysis, the hypothesis for the primary endpoint will be tested at the two-sided 1.64% level ( $p < 0.0164$ ) (O'Brian and Fleming, East 6.5, Copyright © 2018 Cytel Inc.) given that information fraction at the efficacy interim analysis is equal to 0.70. The actual information fraction for the efficacy interim will be recalculated at the final analysis as number of adjudicated primary events at the interim divided by total number of actual primary events for the trial. The two-sided  $\alpha$  level for the final analysis will be recalculated using East 6.5 if information fraction rounded to 2 decimal places is not equal to 0.70.

The DMC will notify the sponsor if the formal stopping criteria for superiority or futility are met.

## 7 APPENDIX 1: MISSING DATE IMPUTATION RULES

### (a) Missing data imputation for AEs

Missing scenario	Imputation rule
If only the day part of the AE onset date is missing	If the month and year are the same as that of first dose of study medication, the date of first dose of study medication will be used as the onset date of the AE. Otherwise, the first day of the month will be used to complete the onset date of the AE
If the day and month parts of the AE onset date are missing	If the year is the same as that of the first dose of study medication, the date of the first dose of study medication will be used as the onset date of the AE. Otherwise, January 1st will be used to complete the onset date of the AE.
If the AE onset date is completely missing and end date missing, or after first dose of study medication	The date of the first dose of study medication will be used as the onset date of the AE.
If only the day part of the AE end date is missing	The last day of the month will be used to complete the end date of the AE.
If the day and month parts of the AE end date are missing	December 31st will be used to complete the end date of the AE.
If the end date of the AE is completely missing and the AE is not ongoing, and the onset date of the AE occurs after the date of the first dose of study medication	Then the onset date of the AE will be used as the AE end date. Otherwise, the date of the first dose of study medication will be used as the AE end date.

(b) Missing data imputation for concomitant medications dates

Start Date	Stop Date	Imputation rule
Known	Partial	Impute stop date as latest possible date (i.e., last day of month if day unknown or 31st December if day and month are unknown).
Known	Missing	Assume on-going
Partial	Known	Impute start date as earliest possible date (i.e., first day of month if day unknown or 1st January if day and month are unknown)
Partial	Partial	Impute start date as earliest possible date (i.e., first day of month if day unknown or 1st January if day and month are unknown) and impute stop date as latest possible date (i.e., last day of month if day unknown or 31st December if day and month are unknown)
Partial	Missing	Assume on-going
Missing	Known	If stop date $\geq$ randomisation date, assign as concomitant
Missing	Partial	Impute stop date as latest possible date (i.e., last day of month if day unknown or 31st December if day and month are unknown)
Missing	Missing	Assume on-going

## APPENDIX 2: TIPPING POINT ANALYSIS

Missing data in the context of the primary analysis is defined as the time interval between the premature censoring date and SED or date of non-sudden cardiac death, whichever came first. Tipping point analysis will be conducted to assess the robustness of the statistically significant results of the primary endpoint. Following steps will be used in tipping point analysis.

### **Step 1. Identification of patients and time interval requiring imputation**

Randomized patients (the FAS population) with a censoring date prior to SED, regardless of the reason for incomplete follow-up (except death), will be flagged as requiring imputation. The time interval subjected to imputation will be defined by the censoring date and SED or date of death, whichever was earlier.

### **Step 2. Estimation of placebo and SJC event rates**

The placebo event rate will be estimated based on available follow-up data among all placebo patients using accelerated failure time model (LIFEREG in SAS). Based on the estimated placebo event rate, the SJC event rate will be estimated as placebo event rate multiplied by the estimated hazard ratio in the primary analysis.

The estimated event rates will be used to inform the time to event in the next step.

### **Step 3. Estimation of event time**

For patients requiring imputation, the event time will be estimated separately within placebo and active treatment groups, based on exponential distribution using corresponding rate parameters. A seed will be used in exponential random generator of event time.

Simulated follow-up time (placebo) =  $360 * (RV / ER_{placebo})$

Simulated follow-up time (SJC) =  $360 * (RV / (ER_{placebo} * Hazard Ratio))$

Where RV = exponential random variate ( $\lambda=1$ ),  $ER_{placebo}$  = Placebo event rate, Hazard Ratio=hazard ratio from primary analysis.

### **Step 4. Imputation of events**

A simulated date of event is defined as the original censoring date plus the simulated time to event. If the simulated date of event is prior to both SED and the date of death, if applicable, an event will be imputed for this patient with the new time to event calculated based on the simulated date of event. Otherwise the patient will be censored at SED or the date of death, whichever is earlier.

**Step 5. Combining results from imputations**

Step 4 will be repeated 1000 times, generating 1000 imputed datasets. Each of the imputed dataset together with the observed data for the patients with complete follow-up will be analyzed using the same Cox proportional hazards model as the primary analysis. The 1000 hazard ratio estimates will be then combined using the Rubin's combination rule (PROC MIANALYZE). Hazard ratio, 95% CI and p-value will be reported.

**Step 6. Identifying the tipping point**

The imputations in Step 4 will be repeated while SZC event rates will be systematically increased in small increments from observed rates. Placebo event rates will be held at observed rates. The p-value from the combined results will be compared to the alpha threshold for primary analysis. The process will be repeated until the tipping point, as expressed as the ratio of the assumed event rate between the active and placebo groups, is found where the statistical significance is lost.

## APPENDIX 3: ATC TERMS FOR POTASSIUM BINDERS

ATC CODE	RECNO	SEQNO1	SEQNO2	INGREDIENTS
V03AE	000677	01	001	SODIUM POLYSTYRENE SULFONATE
V03AE	003281	01	001	CALCIUM POLYSTYRENE SULFONATE
V03AE	075390	01	001	PATIROMER
V03AE	075390	02	001	PATIROMER CALCIUM
V03AE	075390	03	001	PATIROMER SORBITEX CALCIUM
V03AE	087714	01	001	SODIUM ZIRCONIUM CYCLOSILICATE

